8.2.4. Hospitalization

Hospitalization is defined as any initial admission (even less than 24 hours) in a hospital or equivalent healthcare facility, or any prolongation of an existing admission. Admission also includes transfer within the hospital to an acute/intensive care unit (eg, from the psychiatric wing to a medical floor, medical floor to a coronary care unit, or neurological floor to a tuberculosis unit). An emergency room visit does not necessarily constitute a hospitalization; however, the event leading to the emergency room visit is assessed for medical importance.

Hospitalization does not include the following:

- Rehabilitation facilities;
- Hospice facilities;
- Respite care (eg, caregiver relief);
- Skilled nursing facilities;
- Nursing homes;
- Same-day surgeries (as outpatient/same-day/ambulatory procedures).

Hospitalization or prolongation of hospitalization in the absence of a precipitating clinical AE is not in itself an SAE. Examples include:

- Admission for treatment of a preexisting condition not associated with the development of a new AE or with a worsening of the preexisting condition (eg, for workup of a persistent pretreatment laboratory abnormality);
- Social admission (eg, subject has no place to sleep);
- Administrative admission (eg, for yearly physical examination);
- Protocol-specified admission during a study (eg, for a procedure required by the study protocol);
- Optional admission not associated with a precipitating clinical AE (eg, for elective cosmetic surgery);
- Hospitalization for observation without a medical AE;
- Preplanned treatments or surgical procedures. These should be noted in the baseline documentation for the entire protocol and/or for the individual subject.

Diagnostic and therapeutic noninvasive and invasive procedures, such as surgery, should not be reported as SAEs. However, the medical condition for which the procedure was performed should be reported if it meets the definition of an SAE. For example, an acute appendicitis that begins during the reporting period should be reported if the SAE requirements are met, and the resulting appendectomy should be recorded as treatment of the AE.

8.3. Severity Assessment

If required on the AE page of the CRF, the investigator will use the adjectives MILD, MODERATE, or SEVERE to describe the maximum intensity of the AE. For purposes of consistency, these intensity grades are defined as follows:		
MILD	Does not interfere with subject's usual function.	
MODERATE	Interferes to some extent with subject's usual function.	
SEVERE	Interferes significantly with subject's usual function.	

Note the distinction between the severity and the seriousness of an AE. A severe event is not necessarily an SAE. For example, a headache may be severe (interferes significantly with the subject's usual function) but would not be classified as serious unless it met one of the criteria for SAEs, listed above.

8.4. Special Situations

8.4.1. Protocol-Specified Serious Adverse Events

Unless the investigator believes that there is a causal relationship between the investigational product and an event specified below, these events should not be reported to Pfizer Safety by the investigator as SAEs. These events are anticipated to occur commonly in a population with DMD. However, these events should still be recorded as AEs on the CRF.

Protocol-specified SAEs that will not normally be reported to Pfizer Safety in an expedited manner:

- 1. Loss of mobility or ambulation;
- 2. Muscle weakness;
- 3. Symptoms related to spinal deformity;
- 4. Respiratory muscle weakness/Hypoxia;
- 5. Fracture;
- 6. Steroid related metabolic changes (eg, hypertension, diabetes).

Should an aggregate analysis indicate that these pre-specified events occur more frequently than expected, eg, based on epidemiological data, literature, or other data, then this will be submitted and reported in accordance with Pfizer's safety reporting requirements. Aggregate analyses of safety data will be performed on a regular basis per internal standard operating procedures.

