Although it has not been described, either in previous dystrophin gene therapy clinical trials, or in pre-clinical models, a cellular immune response to newly and widely expressed dystrophin could theoretically induce local tissue damage related to the site of new protein expression, which would have the potential for clinical manifestation as a myositis or myocarditis. Both will be difficult to monitor in the setting of DMD, given the degree of ongoing muscle and myocardial damage related to the disease but will require a low threshold for diagnostic consideration.

A diagnosis of myositis might be considered in the event of evidence of increasing muscle pain or weakness associated with a rising creatine kinase (CK) or C-reactive protein (CRP). MRI and comparison to baseline scans may aid in the diagnosis. Myocarditis may be considered in the event of increased or new cardiac symptoms, an increased cardiac troponin I (cTnI) and creatine kinase myocardial b fraction (CK-MB), CRP, or as evidenced on electrocardiogram (ECG) or cardiac MRI (or echocardiogram).

Furthermore, the study will utilize an external data monitoring committee (E-DMC) to provide an objective assessment of safety, and which may include an expert in clinical immunopharmacology (eg, clinical immunologist, rheumatologist, transplant physician) for *ad hoc* consultation should the need arise (Section 9.6).

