3.5. Dose Progression and Stopping Rules

As described above (Section 3.1), 2 cohorts are planned in this study. The available results of the 2-month muscle biopsies of the enrolled subjects will be reviewed prior to dosing the 4th subject in the low-dose cohort, and in either of the following cases, an *ad hoc* E-DMC review of the available cumulative safety data may be requested to assess whether escalation to the high-dose cohort may commence:

1. No measurable transgene (mini-dystrophin) noted in 2 of the first 3 enrolled subjects, or

2. Level of transgene expression is regarded by the sponsor as inadequate to translate into functional benefit.

If adequate transgene expression is observed, dosing of the remaining subjects in the low-dose cohort will continue as planned, after which an E-DMC review of available cumulative safety data will occur.

In any circumstance, progression to the high-dose cohort will not proceed until the first dose level is deemed safe by the E-DMC, principal investigators and sponsor study team.

If no transgene (mini-dystrophin) expression is observed in any of the 2-month biopsies from the low-dose cohort, then prior to dosing the 4th subject in the high-dose cohort, all available biopsies may be assessed. If these samples are also negative for transgene (mini-dystrophin) expression, an *ad hoc* E-DMC review of the available cumulative safety data may be requested to determine whether the study should be terminated.

For both cohorts and at any dose level of PF-06939926, if one of the following safety issues occurs, further enrollment will be halted until the E-DMC reviews data for the subjects with the clinical events that prompted the review and makes recommendations as to next steps:

- Any potentially treatment-related serious adverse event (SAE);
- Similar clinically significant safety findings in ≥50% of subjects at a given dose level, indicating dose-limiting intolerance;
- Repeated alkaline phosphatase or total bilirubin $>2 \times$ the upper limit of normal (ULN);
- Any set of laboratory results meeting Hy's Law (see Section 8.4.2 for Hy's Law criteria);
- Clinical diagnosis of myositis or myocarditis;
- Other findings that, at the discretion of the sponsor study team, investigator and/or E-DMC, indicate that dose escalation should be halted or that dose de-escalation would be appropriate.

Additional information on the E-DMC can be found in Section 9.6.

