8.1.5. Causality Assessment

The investigator's assessment of causality must be provided for all AEs (serious and non-serious); the investigator must record the causal relationship on the CRF, and report such an assessment in accordance with the SAE reporting requirements, if applicable. An investigator's causality assessment is the determination of whether there exists a reasonable possibility that the investigational product caused or contributed to an AE; generally the facts (evidence) or arguments to suggest a causal relationship should be provided. If the investigator does not know whether or not the investigational product caused the event, then the event will be handled as "related to investigational product" for reporting purposes, as defined by the sponsor. If the investigator's causality assessment is "unknown but not related" to investigational product, this should be clearly documented on study records.

In addition, if the investigator determines that an SAE is associated with study procedures and/or concomitant medications or therapies, the investigator must record this causal relationship in the source documents and CRF, and report such an assessment in the dedicated section of the CT SAE Report Form and in accordance with the SAE reporting requirements.

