9.1. Sample Size Determination

The total sample size of up to 22 subjects across 2 dose cohorts, of 2 sub-populations (ambulatory and non-ambulatory) and the sirolimus cohort is based on clinical considerations to provide adequate safety, tolerability, and pharmacodynamics (PD) information at each dose level for both ambulatory and non-ambulatory subjects.

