- metabolic disorders (hyperlipidaemia, hypertriglyceridaemia, dyslipidaemia);
- skin conditions (skin rash, skin erosion, skin irritation);
- increased susceptibility to infection (label warning: herpes zoster, bacterial pneumonia, sepsis, septic shock, cellulitis);
- liver abnormalities (hepatic function abnormal, increased ALT and/or AST);
- impaired healing (also in Warnings and Precautions);
- pyrexia;
- swelling/edema.

As per the warnings in the sirolimus label, there is a potential risk of angioedema with sirolimus alone, and with concomitant use of ACE inhibitors. If angioedema were to occur in this study during treatment with sirolimus, sirolimus dosing should be discontinued immediately. Subjects with angioedema prior to infusion with PF-06939926 will be withdrawn from this cohort. The following AEs may be challenging to evaluate for relatedness if they occur during the co-administration period, since they have been reported for both sirolimus and PF-06939926 during the first 2 weeks of administration: hypertension, anemia, nausea, diarrhea, headache, fever, thrombocytopenia, hemolytic uremic syndrome, thrombotic microangiopathy.

Cohort Intervention: Subjects in this cohort will receive oral sirolimus solution as follows:

Subject Age/ Weight Range	≤40.0 kg	>40.0 kg
Day -10 before PF-06939926 infusion	Oral sirolimus solution at loading dose of 2.25 mg/m ² BSA given twice daily.	Oral sirolimus solution at loading dose 3 mg given twice daily.
Day -9 to Day -1 (or sooner if dose adjustment is required based on	Oral sirolimus solution at maintenance dose of 0.75 mg/m ² BSA given twice daily.	Oral sirolimus solution at maintenance dose of 1 mg given twice daily.
the Day -7 trough concentration level) before PF-06939926	Day -7 before PF-06939926 infusion: Draw blood to measure sirolimus trough concentration (local lab).	Day -7 before PF-06939926 infusion: Draw blood to measure sirolimus trough concentration (local lab).
infusion and on the morning of Day 1.		

Subject Age/ Weight Range	≤40.0 kg	>40.0 kg			
Weight Range	5	Ü			
	If trough concentration is	If trough concentration is			
Based on the	<3.9 ng/mL, increase dose by the	<3.9 ng/mL, increase dose by			
Day -7 sirolimus	following formula: current dose ×	the following formula: current			
trough	(5.5 ng/mL ÷ current	dose \times (5.5 ng/mL \div current			
concentration,	concentration).	concentration).			

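### The Section 8.4.1 exemption from expedited SAE reporting turns on the investigator believing the product caused the event, which conflicts with Sections 8.1, 8.1.4.1, 8.1.5 and 3.5 when the cause is uncertain

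*Protocol*

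**What the plan says.** Protocol Section 8.4.1 names six kinds of event that are expected to be common in DMD. Its condition is "Unless the investigator believes that there is a causal relationship between the investigational product and an event specified below"; failing that, "these events should not be reported to Pfizer Safety by the investigator as SAEs". Item 2 is simply "Muscle weakness". Respiratory muscle weakness or hypoxia is also listed without qualification. Hypertension appears only as an example of a steroid-related metabolic change. The events still go on the CRF as AEs. No time window after infusion is given. Section 8.1 refers forward to this list and again makes reporting depend on the investigator judging that there is a causal link.

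Four other parts of the protocol bear on the same report:

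- Section 8.1 requires SAEs to reach Pfizer Safety within 24 hours of awareness, whatever the investigator thinks about relatedness. Section 8.1.4.1 requires the same report for every SAE in the active collection period.
- Section 8.1.5 says: "If the investigator does not know whether or not the investigational product caused the event, then the event will be handled as" related to the product for reporting purposes.
- Section 3.5 halts enrollment pending E-DMC review for "Any potentially treatment-related serious adverse event (SAE", among other triggers.
- Section 1.5.2 says "A diagnosis of myositis might be considered in the event of evidence of increasing muscle pain or weakness" together with a rising CK or CRP. Appendix 1 says certain events may be hard to attribute during sirolimus co-administration, "since they have been reported for both sirolimus and PF-06939926 during the first 2 weeks of administration: hypertension" and several others.

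**The concern.** The exemption asks for positive belief in causation. The halt asks only whether a relation is possible, and the general causality rule resolves doubt towards related. These tests part company for the investigator who sees early serious weakness or hypertension and cannot say whether it is disease, steroid or vector.

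Section 1.5.2 concedes that immune myositis would be difficult to monitor against the background of DMD and asks for a low threshold for considering it. Under Section 5, subjects are also to take prednisone or prednisolone at ≥2 mg/kg/day in the first two weeks, so a steroid explanation for hypertension is readily at hand. If the investigator follows the wording of 8.4.1, the event is recorded as an AE on the CRF without a 24-hour report. Prompt review of a single serious event, which is what a small dose-escalation study relies on, could then be delayed.

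**Working it through.** The planned size of up to 22 subjects "is based on clinical considerations to provide adequate safety, tolerability, and pharmacodynamics (PD) information at each dose level", so there is no power or error-rate figure to reproduce. The check is mainly textual.

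**1. What each rule requires for a listed serious event**

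| Investigator's view | 8.4.1 and its cross-reference in 8.1 | 8.1.5 | General rule in 8.1 and 8.1.4.1 | 3.5 test |
|---|---|---|---|---|
| Believes related | Report | Related | Report | Met |
| Does not know | Do not report, on the wording | Handle as related | Report | Met on a natural reading |
| Judges unrelated | Do not report | Not related | Report | Not met on that view |

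The rules agree in the first row. In the third, 8.4.1 is a deliberate exception that 8.1 acknowledges, although 8.1.4.1 does not mention it. The second row is the real conflict: someone who does not know does not believe, so 8.4.1 and 8.1.5 point in opposite directions, and neither says which prevails.

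**2. Whether the second row is likely to be used**

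- Muscle weakness: Section 1.5.2 makes it, with rising CK or CRP, a possible sign of a myositis that it calls theoretical and hard to monitor in DMD.
- Hypertension: Appendix 1 says it has been reported for both PF-06939926 and sirolimus in the first 2 weeks and may be hard to attribute.
- Respiratory weakness or hypoxia: listed without limit, but no passage found names it as a product harm.

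**3. Whether another halt trigger would catch a single event**

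- Section 3.5 halts separately for a clinically diagnosed myositis or myocarditis. This needs no SAE form, but it needs the diagnosis, which follows the weakness.
- It halts for similar significant findings in at least 50% of subjects at a dose level. SAP Section 2.5 gives high-dose groups of 16 and 3. 16 + 3 = 19 and 19 × 0.5 = 9.5, so at least 10 subjects are needed once the group is full. Earlier in accrual the denominator is smaller and fewer would suffice.
- It halts for other findings at the discretion of the sponsor, investigator or E-DMC, which requires someone to have noticed them.

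**4. What a delay could have meant during dosing**

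The documents give no time from CRF entry to review. Assume a lag L of 1 to 4 weeks and a dosing interval d; the further infusions before review are about L ÷ d, rounded down. At d = 1 week this is 1 to 4. At d = 2 weeks it is 0 to 2, and at d = 3 weeks 0 to 1. Section 3.1 allows the 1-week interval only after six consecutive subjects at a dose level without a stopping or pause criterion, and with E-DMC agreement. The range illustrates the assumption; it is not an estimate.

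**5. What remains open now**

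SAP Section 2.5 states that 22 participants received a dose, which is the protocol's maximum. Follow-up runs to 5 years, and Section 8.1.4 narrows collection in Years 2 to 5 to SAEs and AEs believed related. How a listed event is classified therefore still matters.

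**The case against.** The strongest reply is that 8.1.5 already covers the unsure investigator. It is a reporting rule, no passage says 8.4.1 overrides it, and read together the unsure case is reported. On that reading the gap shrinks to events judged unrelated, where an exemption for expected disease events is ordinary practice. This is a fair reading, but not the only one: the text specific to these events, in 8.4.1 and in the 8.1 cross-reference, repeats the positive test, and a site could reasonably follow the specific text.

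Other safeguards also stand. Listed events stay on the CRF. Aggregate analyses are regular. Subjects stay near the site through Day 14, with visits on Days 4, 7 and 10 and local laboratory tests on Days 5 to 9. The E-DMC reviews aggregate safety and serious AE data. These make a lost event unlikely, although 8.4.1 does not say whether a listed event recorded as an AE keeps its serious classification for that review.

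A reader might infer more than the documents support:

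- That hypertension in general is exempt. Only steroid-related hypertension is listed.
- That the protocol names muscle weakness as a product harm. It names weakness with rising CK or CRP as a possible sign of a myositis that it says has not been described in earlier dystrophin gene therapy trials or preclinical models.
- That Appendix 1 speaks to vector versus steroid. It concerns co-administration with sirolimus, which one participant received.
- That the halt runs only through the Pfizer Safety form. No passage says so; the link is an inference.

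**Conclusion.** The point holds as an inconsistency in reporting rules. For a listed serious event of uncertain cause, 8.4.1 and 8.1.5 give opposite instructions. The 8.4.1 exemption also departs from the all-SAE rule and sits uneasily with the wider test in 3.5. It has no time limit and covers events that the protocol itself calls hard to attribute. The consequence is a possible delay in expedited review of a serious event recorded only as a CRF AE.

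Its size cannot be given as a rate. The 1 to 4 further infusions in the working rest wholly on an assumed lag. With all 22 participants dosed, the effect on enrollment halts is mainly retrospective. The documents do not show that any event was missed or any halt failed, and that should not be read into this point. What continues is ambiguity about reporting through follow-up. This is a modest, inexpensive correction.

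**What to change.** Reconcile Section 8.4.1, and the cross-reference to it in 8.1, with the all-SAE rule in 8.1 and 8.1.4.1, the causality rule in 8.1.5, the risk text in 1.5.2 and Appendix 1, and the wording of 3.5. In 8.4.1, state that 8.1.5 governs when causality is unknown, so the exemption does not apply and the event is reported within 24 hours.

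The sponsor and E-DMC should also state whether the exemption covers the early post-infusion period, and how listed events relate to the SAE wording in 3.5. The content of any halt rule is theirs to decide, and none is proposed here.

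Cost: one or two sentences, with no new visits, tests or staff. The downside is a few extra expedited reports for events that prove to be DMD or steroid effects.

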8.4.2. Potential Cases of Drug-Induced Liver Injury

Humans exposed to a drug who show no sign of liver injury (as determined by elevations in transaminases) are termed "tolerators," while those who show transient liver injury, but adapt are termed "adaptors." In some subjects, transaminase elevations are a harbinger of a more serious potential outcome. These subjects fail to adapt and therefore are "susceptible" to progressive and serious liver injury, commonly referred to as drug-induced liver injury (DILI).

In the majority of DILI cases, elevations in aspartate aminotransferase (AST) and/or alanine aminotransferase (ALT) precede total bilirubin (TBili) elevations (>2 × ULN) by several days or weeks. The increase in TBili typically occurs while AST/ALT is/are still elevated above 3 × ULN (ie, AST/ALT and TBili values will be elevated within the same lab sample). In rare instances, by the time TBili elevations are detected, AST/ALT values might have decreased. This occurrence is still regarded as a potential DILI. Therefore, abnormal elevations in either AST OR ALT in addition to TBili that meet the criteria outlined below are considered potential DILI (assessed per Hy's law criteria) cases and should always be considered important medical events, even before all other possible causes of liver injury have been excluded.

The threshold of laboratory abnormalities for a potential DILI case depends on the subject's individual baseline values and underlying conditions. Subjects who present with the following laboratory abnormalities should be evaluated further as potential DILI (Hy's law) cases to definitively determine the etiology of the abnormal laboratory values:

- Subjects with AST/ALT and TBili baseline values within the normal range who subsequently present with AST OR ALT values >3 × ULN AND a TBili value >2 × ULN with no evidence of hemolysis and an alkaline phosphatase value <2 × ULN or not available.
- For subjects with baseline AST **OR** ALT **OR** TBili values above the ULN, the following threshold values are used in the definition mentioned above, as needed, depending on which values are above the ULN at baseline:
 - Preexisting AST or ALT baseline values above the normal range: AST or ALT values >2 times the baseline values AND >3 × ULN; or >8 × ULN (whichever is smaller).
 - Preexisting values of TBili above the normal range: TBili level increased from baseline value by an amount of at least 1 × ULN **or** if the value reaches >3 × ULN (whichever is smaller).

Rises in AST/ALT and TBili separated by more than a few weeks should be assessed individually based on clinical judgment; any case where uncertainty remains as to whether it represents a potential Hy's law case should be reviewed with the sponsor.

In addition, however, as described in Section 1.5.1, in DMD patients, the standard biomarkers of the onset of hepatocellular injury such as ALT and AST are not capable of detection of liver damage due to the release of these enzymes from diseased skeletal muscle. To address the shortcoming, elevations of GLDH >2 x ULN will also be assessed individually based on clinical judgment and with the support of the *ad hoc* hepatic and/or immunopharmacologic expert (s) supporting the E-DMC; any case where uncertainty remains as to whether it represents a potential Hy's law case should be reviewed with the sponsor. Subjects who experience a consistent GLDH elevation above 3 × ULN may also be monitored more frequently to determine if they are an "adaptor" or are "susceptible", as defined above.

If any of the above criteria is met, the subject should return to the investigator site and be evaluated as soon as possible, preferably within 48 hours from awareness of the abnormal results. This evaluation should include laboratory tests, detailed history, and physical assessment.

In addition to repeating measurements of AST and ALT and TBili, laboratory tests should include albumin, creatine kinase (CK), direct and indirect bilirubin, gamma-glutamyl transferase (GGT), GLDH, prothrombin time (PT)/international normalized ratio (INR), total bile acids, alkaline phosphatase and acetaminophen drug and/or protein adduct levels.

Consideration should also be given to drawing a separate tube of clotted blood and an anticoagulated tube of blood for further testing, as needed, for further contemporaneous analyses at the time of the recognized initial abnormalities to determine etiology. A detailed history, including relevant information, such as review of ethanol, acetaminophen (either by itself or as a co-formulated product in prescription or over-the-counter medications), recreational drug, supplement (herbal) use and consumption, family history, sexual history, travel history, history of contact with a jaundiced person, surgery, blood transfusion, history of liver or allergic disease, and potential occupational exposure to chemicals, should be collected. Further testing for acute hepatitis A, B, C, D, and E infection and liver imaging (eg, biliary tract) may be warranted.

All cases demonstrated on repeat testing as meeting the laboratory criteria of AST/ALT and TBili elevation defined above should be considered potential DILI (Hy's law) cases if no other reason for the liver function test (LFT) abnormalities has yet been found. Such potential DILI (Hy's law) cases are to be reported as SAEs, irrespective of availability of all the results of the investigations performed to determine etiology of the LFT abnormalities.

A potential DILI (Hy's law) case becomes a confirmed case only after all results of reasonable investigations have been received and have excluded an alternative etiology.

8.4.3. Exposure to the Investigational Product during Pregnancy or Breastfeeding, and Occupational Exposure

Exposure to the investigational product under study during pregnancy or breastfeeding and occupational exposure are reportable to Pfizer Safety within 24 hours of investigator awareness.

